# 5.2 Primary Effectiveness Endpoint

The primary effectiveness endpoint is technical success. The technical success is defined as the ability of the FreedomFlowTM Orbital Atherectomy System to achieve a residual diameter stenosis  $\leq 50\%$  immediately post treatment without adjunctive balloon inflation, as assessed by an independent Angiographic Core Laboratory.

# 5.3 Secondary Endpoints

# **5.3.1** Secondary Safety Endpoints

- Hemoglobin, hematocrit, and free hemoglobin (pre-procedure, immediately postprocedure, and at discharge) will be measured and reported.
- All device and procedure related serious adverse events at 30 days and 6 months post procedure.

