#### 2.1.1 Control Module

The Control Module, Model CM1001, is a portable, reusable component of the system that integrates delivery of saline and pneumatic power to the User Handle. The Control Module touchscreen is the primary interface for operating the peristaltic pump and regulating orbital speed of the User Handle. The pre-programmed Control Module includes a pneumatic pressure hose and hospital-grade electrical plug. The Control Module can be placed on a table or mounted to a standard 5-wheel IV pole.

[figure not shown]

Figure 2-2: Control Module

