# 4.2 Sample Size and Number of Centers

The study may enroll up to 10 subjects and will be conducted at up to 2 investigational sites in the United States.

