## **Changing a Saline Infusion Bag**

To change a saline infusion bag during a procedure, the operation must be paused. If the peristaltic pump door is opened during a procedure, pneumatic power to the User Handle will cease immediately.

- 1. Remove the User Handle and driveshaft from patient (see instructions above).
- 2. Turn off peristaltic pump by tapping the OFF icon on the Control Module touch screen.
- 3. Disconnect current saline infusion bag from IV spike on the Tubing Set and hold the spike upward to prevent the introduction of air.
- 4. Without touching the sterile IV spike tip, insert a new saline infusion bag onto the IV spike and rehang on the IV pole.
- 5. Repeat a complete flush cycle of the User Handle and driveshaft.

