#### **6.5.4** Procedure Medications

Warning: Performing atherectomy in the presence of severe arterial spasm can result in vessel dissection or perforation. If severe spasm is observed during treatment with the FreedomFlowTM Atherectomy System, immediately stop driveshaft rotation.

Anti-coagulation medication and loading dose of anti-platelet medications will be given prior to the atherectomy procedure per investigational site atherectomy standard procedure. Antispasmodic medications such as nitroglycerine (200  $\mu$ g intra-arterial (IA) bolus; up to 3000  $\mu$ g per subject) or papaverine (300  $\mu$ g IA bolus) may be administered. To avoid frequent IA bolus injections, the following solution (500 ml normal saline with 3000  $\mu$ g heparin, 3000  $\mu$ g nitroglycerin and 2.5 mg Cardizem) can be infused intra-arterially at a rate of 6 mL/min. All medications administered for this study should be recorded in the subject's medical record.

During the procedure, any device malfunction and device/procedure related adverse events, including anaphylaxis to medications or device components will be monitored and recorded.

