#### 8 STATISTICS

This study is a one or two center, prospective, non-randomized single-arm Early Feasibility Study. All clinical endpoints will be summarized with descriptive statistics without hypothesis testing. For continuous variables, the range (minimum, maximum), mean, standard deviation, median, first and third quartiles (Q1 and Q3) may be reported, while for discrete variables, count and percentage will be provided.

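### Hemoglobin, hematocrit and free hemoglobin are summarized as raw concentrations although saline is delivered during the procedure and its volume is not requested; a dilution-invariant hemolysis index would be a nearly free addition

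*Combined protocol and SAP*

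**What the plan says.** Section 5.3.1 sets the endpoint: "Hemoglobin, hematocrit, and free hemoglobin (pre-procedure, immediately postprocedure, and at discharge) will be measured and reported". Section 8 gives the analysis: "All clinical endpoints will be summarized with descriptive statistics without hypothesis testing". Neither section defines a change from the pre-procedure value, a combined measure or any adjustment for fluid given.

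Saline enters the procedure in two ways:

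- **Device saline.** The Control Module (2.1.1) "integrates delivery of saline and pneumatic power to the User Handle", and the Tubing Set (2.1.2) carries it. The instructions on changing a saline bag in 6.5.3 foresee that a bag may run out mid-procedure: "To change a saline infusion bag during a procedure, the operation must be paused". No flow rate or bag size is given.
- **Optional medicated solution.** Section 6.5.4 describes a 500 mL saline-based solution that "can be infused intra-arterially at a rate of 6 mL/min".

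The nearest recording rule is also in 6.5.4: "All medications administered for this study should be recorded in the subject's medical record". It names no volume and does not clearly reach plain device saline. Table 6-1 has no fluid row, and its medications row has no mark in the procedure column.

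**The concern.** A concentration changes when the mass of the analyte changes or when the volume it is dissolved in changes. The procedure can alter both. Retained saline lowers hemoglobin and hematocrit without any blood loss, and it lowers the measured free hemoglobin whether or not red cells have been destroyed. On a raw summary, dilution therefore makes hemolysis look somewhat smaller and a fall in hemoglobin somewhat larger.

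Section 7.2 lists hemolysis and anemia among the possible risks, and after the procedure 6.6 schedules no other laboratory test on either. The study has a single arm, so no control group shares the dilution, and with so few subjects each value will be read individually. The exposed sample is mainly the immediate post-procedure one. Under 6.6 the later sample comes at 12 to 24 hours, or before discharge if that is sooner, so an early discharge narrows the gap.

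**Working it through.** The plan states no figure for this endpoint, so there is nothing to reproduce. The check is a mass balance.

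**Inputs from the documents:** 500 mL for the optional solution and 6 mL/min for its rate (6.5.4). A full 500 mL takes 500 / 6 = 83 minutes.

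**Assumptions not in the documents:** blood volume BV 4-6 L; starting hemoglobin (Hb) 14 g/dL; starting hematocrit (Hct) 42%, so plasma volume PV = 0.58 x BV; fraction of infused saline still in the circulation at sampling 25-100%; total saline infused 18-1000 mL. Retained volume r = volume infused x fraction retained.

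**Formulas if dilution is the only change:**

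- Hb after = Hb before x BV / (BV + r), and the same factor for Hct
- free Hb after = free Hb before x PV / (PV + r)

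**One case in full (BV 5 L, 500 mL infused, all retained):**

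- Hb = 14 x 5 / 5.5 = 12.7 g/dL, a fall of 1.3 g/dL
- Hct = 42 x 5 / 5.5 = 38.2%
- PV = 2.9 L, so the free Hb factor is 2.9 / 3.4 = 0.853, a reading 14.7% low
- The same Hb and Hct would follow a blood loss of 5000 x (1 - 5/5.5) = 455 mL with volume replaced, so these two values cannot tell the explanations apart

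**Ends of the range for 500 mL infused:**

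- Smallest (BV 6 L, 25% retained, r = 0.125 L): Hb falls 14 x (1 - 6/6.125) = 0.29 g/dL; free Hb reads 1 - 3.48/3.605 = 3.5% low
- Largest (BV 4 L, 100% retained, r = 0.5 L): Hb falls 14 x (1 - 4/4.5) = 1.56 g/dL; free Hb reads 1 - 2.32/2.82 = 17.7% low

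**Other infused volumes, same assumptions:**

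| Saline infused | Fall in Hb (g/dL) | Free Hb reads low by |
|---|---|---|
| 18 mL (3 minutes at 6 mL/min) | 0.01-0.06 | 0.1-0.8% |
| 250 mL | 0.14-0.82 | 1.8-9.7% |
| 500 mL | 0.29-1.56 | 3.5-17.7% |
| 1000 mL | 0.56-2.80 | 6.7-30.1% |

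**Thresholds.** A 1 g/dL fall from dilution alone needs r = BV x (14/13 - 1), about 0.31-0.46 L retained. Halving free Hb needs r = PV, about 2.3-3.5 L retained. At the upper end for 500 mL, a true threefold rise in free Hb would still read as 3 x (1 - 0.177) = 2.5-fold.

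**Why the index is unaffected by dilution.** If free Hb is measured in plasma, free Hb x (1 - Hct) is the mass of free Hb divided by BV, and total Hb is the total mass divided by BV. The volume cancels in the ratio. In the worked case with an undiluted free Hb of 50 mg/dL (0.050 g/dL):

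- before: 0.050 x 0.58 / 14 = 0.207%
- after, with free Hb diluted to 42.6 mg/dL: 0.0426 x 0.618 / 12.73 = 0.207%

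**The case against.** The strongest reply is that the size is entirely assumed. No section gives a device flow rate, a bag size or the amount of saline that reaches the circulation, and some of it is flush that never enters the subject. The only stated volume belongs to an optional solution that takes 83 minutes to run in full. This stands: the effect could be negligible, and the 1000 mL row has no basis in the documents.

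Second, the endpoint only promises to measure and report. A measured hemoglobin is the subject's actual concentration at that time and misleads only if it is read as red-cell loss. This also stands as a limit, but readers of a first-in-human safety report are likely to read it that way.

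Third, the collection gap is only partly shown. The amount of the optional solution may be recoverable from the medical record. The case report forms are not part of the documents. Run time and balloon pressure are endpoints in 5.3.2 without a row in Table 6-1, so a missing row does not prove that the form omits fluid volume. What remains is that nothing in the protocol requires the volume, most clearly for device saline.

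A reader might also infer three stronger points that the documents do not support:

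- **That hemolysis could be missed.** A reading 4-18% low does not conceal a several-fold rise.
- **That the bias grows with device use.** No section ties saline volume to run time, and the optional solution's volume follows infusion time.
- **That the three measured values cancel dilution throughout.** They do so only for free hemoglobin, and only if it is measured in plasma. Sections 5.3.1, 6.4 and 6.6 do not name the specimen.

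**Conclusion.** The point holds as a minor one. The three analytes are summarized as raw concentrations, saline is delivered during the procedure, and the protocol does not ask how much. The direction of the bias is certain for whatever volume is retained; its size is not. Under the stated assumptions, 500 mL infused lowers hemoglobin by about 0.3-1.6 g/dL and free hemoglobin by about 4-18%, mainly at the immediate post-procedure draw. The hemoglobin effect could matter when one subject's fall is interpreted. The free hemoglobin effect is modest.

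No error rate, sample size or decision rule changes, because the endpoint is secondary and descriptive in at most 10 subjects. The reason to act is that the remedy costs almost nothing and that device saline volume, if not recorded at the procedure, may not be recoverable later.

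**What to change.** In 5.3.1 and Section 8:

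- Keep the raw values at each time point, and add each subject's paired change from pre-procedure.
- Add, as a supplementary hemolysis measure, percent hemolysis = plasma free hemoglobin x (1 - hematocrit) / total hemoglobin x 100. Take all three values from the same draw, with both hemoglobin measures in the same unit and hematocrit as a fraction, and state that free hemoglobin is measured in plasma.

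On the procedure case report form, record total saline volume: device saline plus any intra-arterial solution. List it beside each subject's hemoglobin and hematocrit changes as context.

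State the limit in the report: the index addresses free hemoglobin only, and because retention is unknown, neither the index nor the infused volume fully separates dilution from blood loss with volume replaced.

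The cost is one derived variable from values already drawn and one form field, with no added test or blood draw. The field should be in place before the first procedure.

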## **5.3.2** Secondary Effectiveness Endpoints

- Clinical Success, defined as the ability of the FreedomFlow™ Orbital Atherectomy System to achieve a final residual diameter stenosis ≤50% with or without adjunctive low pressure balloon therapy, determined by independent angiographic core laboratory.
- Procedure Success, defined as:
  - No procedure-related MAE
  - $\circ$   $\leq$  50% residual stenosis at target lesion
  - No device malfunction causing the procedure to be aborted
- Percent of device run time less than 3 minutes cumulative total
- Maximum balloon inflation pressure with adjunctive plain balloon angioplasty and/or drug coated balloon angioplasty
- Improvement of ABIs at 30 days and 6 months
- Improvement of Rutherford Classification at 30 days and 6 months.
- Improvement of patient reported outcomes (PRO, VascuQoL questionnaire) at 30 days and 6 months
- Clinical driven target lesion revascularization (TLR), target vessel revascularization (TVR) at 30 days and 6 months (diagnosis of TLR and TVR to be verified by an angiographic core laboratory)
- Primary patency, primary assisted patency and secondary patency at 30 days and 6 months. Patency will be evaluated by duplex ultrasound and evaluated by a Duplex Ultrasound core laboratory). The restenosis is defined as PSVR of 2.5

#### 6 STUDY PROCEDURE

# 6.1 Patient Eligibility, Pre-screening and Exclusions

All patients scheduled for a percutaneous endovascular intervention for PAD in the lower extremity will be screened for study eligibility. A Screening/Enrollment Log will be provided to the study sites, in order to maintain a cumulative tracking of all screened patients.

Subjects must meet all inclusion/exclusion criteria for enrollment in the clinical study. Reasons for screening failure(s) will be documented.

#### 6.1.1 Inclusion Criteria

Subjects must meet ALL of the following criteria to be eligible for participation in the study:

- 1. Age  $\geq$  18 years old.
- 2. Subject is a candidate for percutaneous endovascular intervention for peripheral vascular disease in the lower extremity.
- 3. Disease is located in the common femoral, superficial femoral, populiteal, anterior tibial, posterior tibial, or peroneal artery.
- 4. Objective hemodynamic evaluation that subject has a resting ankle-brachial index (ABI)  $\leq$  0.90, OR subjects with non-compressible arteries (ABI>1.1) must have a toe-brachial index (TBI) of  $\leq$  0.80.
- 5. Clinical presentation of lifestyle limiting claudication or rest pain as characterized by Rutherford Classification 2, 3, 4, or 5.
- 6. Subject has de novo target lesion(s) or lesion(s) treated by percutaneous transluminal angioplasty (PTA) only greater than 3 months prior with stenosis  $\geq$ 70% by visual estimation in the common femoral, superficial femoral, popliteal, anterior tibial, posterior tibial, or peroneal artery. Up to three lesions can be treated at the index procedure provided the cumulative total lesion length is  $\leq$  30 cm AND all lesions are in the same leg.
- 7. Target reference vessel diameter (proximal and distal to target lesion) is 2 to 5 mm by angiographic visual estimation.
- 8. At least one patent vessel run-off to the ankle or foot at baseline.
- 9. The target lesion(s) can be successfully crossed with a commercially available 0.014" atherectomy guidewire without any complications during wiring procedure.
- 10. Subject signs a written Informed Consent form to participate in the study, prior to any study mandated determinations or procedure.

#### 6.1.2 Exclusion Criteria

Subjects must be EXCLUDED from participation in this study if ANY of the following criteria are met:

- 1. Is female with childbearing potential not taking adequate contraceptives or is currently breastfeeding.
- 2. Target lesion is within a native graft or synthetic graft.
- 3. Target lesion is an in-stent restenosis.
- 4. Chronic total occlusion (CTO) with wire crossed near the advential junction.
- 5. Subject has significant stenosis or occlusion of inflow tract (upstream

- disease) not successfully treated during the index procedure and prior to treatment of the target lesion.
- 6. History of an endovascular procedure or open vascular surgery on the index limb within 30 days prior to the index procedure.
- 7. Planned endovascular or surgical procedure within 30 days after the index procedure.
- 8. Signs and symptoms of systemic infection (temperature of  $\geq 38.0^{\circ}$  Celsius and/or WBC of  $\geq 12,000$  cells/ $\mu$ L) at the time of assessment; Note: If infection is adequately treated and controlled (temperature  $< 38.0^{\circ}$  C and WBC < 12,000 cells/ $\mu$ L) patient may be enrolled.
- 9. Unstable coronary artery disease or other comorbid condition(s) that, in the judgment of the physician precludes safe percutaneous intervention.
- 10. Significant acute or chronic kidney disease with a creatinine level > 2.5mg/dL and/or requiring dialysis.
- 11. Evidence or history of intracranial or gastrointestinal bleeding, intracranial aneurysm, myocardial infarction or stoke within 2 months of index procedure.
- 12. Evidence or history of aneurysmal target vessel.
- 13. Clinical/angiographic evidence of distal embolization.
- 14. Known allergy to contrast agents or medications used to perform endovascular intervention that cannot be adequately pre-treated.
- 15. Subjects in whom anti-platelet, anticoagulant, or thrombolytic therapy is contraindicated.
- 16. Heparin-induced thrombocytopenia (HIT) not able to use Bivalirudin.
- 17. Uncorrectable bleeding diathesis, platelet dysfunction, thrombocytopenia with platelet count less than 125,000/mm2, known coagulopathy, or INR > 1.5.
- 18. Thrombolytic therapy within 2 weeks of the index procedure.
- 19. Intra-operative (intra-procedure) clinical or angiographic complication (other than non-flow limiting dissections) attributed to the use of a currently marketed device prior to introduction of the Cardio Flow atherectomy driveshaft.
- 20. Has life expectancy < 12 months.
- 21. Subject is unwilling or unable to comply with the follow-up study requirements.
- 22. Is currently participating in an investigational drug or device study.
- 23. Has one or more stents in the treatment vessel.
- 24. Lacking capacity to provide consent.

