#### 5 STUDY ENDPOINTS

# 5.1 Primary Safety Endpoints

The primary safety endpoint is freedom from a composite of new on-set major adverse events (MAE) through 30-day follow-up as adjudicated by an independent clinical adjudicator.

The components of the MAE are defined as:

- Cardiovascular related death: All cardiovascular cause mortality.
- **Myocardial infarction (MI):** Any newly diagnosed MI post procedure, defined as CK-MB ≥2X upper limit normal (ULN).
- Clinically driven target lesion revascularization (TLR): any repeat percutaneous or surgical intervention to treat objectively documented symptoms of recurrent ischemia attributable to the treated lesion.
- Clinically significant target vessel dissection: NHLBI grade C or greater as confirmed by angiography.
- Clinically significant target vessel perforation: NHLBI Type III as confirmed by angiography.
- **Unplanned major target limb amputation:** Amputation of the transmetatarsals or higher that was not previously planned as part of the overall treatment strategy.
- Clinically relevant distal embolization: Emboli requiring surgical or medical intervention and/or the presence of symptoms.
- **Pseudoaneurysm:** disruption of the arterial wall at the treatment site as confirmed by angiography.

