# 6.5.1 Angiography

At the time of the index procedure, prior to introduction of the Cardio Flow orbital atherectomy device, standard angiography will be performed per the guidelines established by the Angiographic Core Laboratory, to confirm final anatomic eligibility. Subjects who do not meet the final angiographic eligibility criteria, as determined by the investigator at the time of the procedure, will be documented as angiographic screen failures and will not be considered enrolled in the study and no further data will be collected. A subject is considered as "enrolled" after the subject meets all angiographic criteria and a bare-metal atherectomy 0.014" guidewire successfully crosses the target lesion via the true vessel lumen.

Angiography will be performed throughout the procedure to document the treatment outcomes and sent to the sponsor. At a minimum, angiographic images at the following timepoint should be taken.

- Baseline angiography to determine subject's eligibility.
- Post any lesions that are pre-dilated by balloon angioplasty if performed.
- After the Cardio Flow FreedomFlowTM orbital atherectomy treatment session(s).
- Post any adjunctive interventions, e.g. balloon angioplasty and/or stenting, to optimize the outcome or bailout the procedure due to vascular complications.
- Final angiography prior to the end of the procedure.

Up to 3 target lesions are allowed based on the angiographic criteria by this protocol. If 2 or 3 target lesions are selected, the lesion will be numbered based on the anatomic order, i.e. common femoral artery, proximal, middle or distal segment of superficial femoral artery, P1, P2 or P3 segment of popliteal artery, anterior tibial artery, posterior tibial artery, and peroneal artery, regardless of the treatment order.

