# 11.4 Adverse Event Reporting

The signs, symptoms and sequelae of an underlying AE should not be reported as separate AEs. All AEs must be recorded on a CRF. All AEs also must be described by (a) duration (start and resolution dates); (b) adjudicated for severity; (c) relationship to the study device; (d) action taken to resolve the event; (e) outcome of the event; and (f) whether or not such event is considered to

be serious. Additional information, such as procedural notes, treatment notes, or a signed clinical summary, may be required as supporting documentation for the reported AE.

Pre-existing medical conditions or symptoms occurring prior to the start of the atherectomy procedure should not be reported as adverse events. In the situation where there is a worsening of a pre-existing medical condition or symptom due to a study related procedure, an adverse event should be reported.

For any adverse event that is ongoing at the time of the initial report, periodic follow-up information is required until the adverse event is resolved or is judged to be chronically stable. The site should submit relevant follow-up information related to the adverse event as soon as it is available.

Depending upon the nature and seriousness of the adverse event, the sponsor or designee may request the Investigator to provide copies of the subject's medical records (such as the subject's laboratory tests and hospital records, Investigator summaries, etc.) to document the adverse event.

The Investigator will report all serious adverse events, including unanticipated adverse device effects, to the IRB according to the IRB requirements. A copy of this IRB communication should be sent to the Sponsor. In case of an unanticipated adverse device effect occurred, the investigator must report to the Sponsor within 10 working days of the site first becoming aware of the event.

Within 10 working days of notification, the Sponsor will report all unanticipated adverse device effects to the appropriate authority, all participating investigators, and all reviewing IRBs. The Sponsor will ensure that safety reporting for the study is conducted in compliance with all pertinent requirements and regulations.

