# 12.2 Clinical Adverse Event Adjudication

An Independent Adverse Event Adjudicator will be responsible for the adjudication of any events. For this small-scale feasibility study, one physician independent of the study or the sponsor will be responsible for the adjudication of any events that may be considered serious and/or device related by the principal investigator and/or study Sponsor. The physician will be familiar with PTA procedures who is not an investigator in the trial. The adjudication process will include determination of whether the event or device deficiency constitutes a SAE or an UADE, or contributes to the endpoint, and whether the subject should be considered a Procedural Success. All available data (including lab reports, films, discharge reports, etc.) will be available to adjudicate the events.

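### Exclusion 19 tolerates a pre-device dissection with no NHLBI grade cap, so a device injury at the same site could be hard to attribute in the primary safety endpoint

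*Combined protocol and SAP*

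**What the plan says.** **Entry.** Section 6.1.2, exclusion 19 (repeated in the synopsis), bars a "clinical or angiographic complication (other than non-flow limiting dissections) attributed to the use of a currently marketed device" occurring before the study driveshaft is introduced. A dissection within the exception is tolerated whatever its grade. Exclusion 13 separately bars "Clinical/angiographic evidence of distal embolization".

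**Endpoint.** Section 5.1 counts "new on-set major adverse events (MAE) through 30-day follow-up". The relevant component is "Clinically significant target vessel dissection: NHLBI grade C or greater as confirmed by angiography". Flow is not mentioned. Section 5.3.2 carries the same classification into Procedure Success through "No procedure-related MAE".

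**Timing.** Section 11 starts adverse event documentation once treatment has been initiated. Section 11.4 adds: "Pre-existing medical conditions or symptoms occurring prior to the start of the atherectomy procedure should not be reported as adverse events". It makes worsening of such a condition reportable when a study-related procedure caused it.

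**Images and adjudication.** The minimum angiogram list in section 6.5.1 includes "Post any lesions that are pre-dilated by balloon angioplasty if performed", and a separate image after atherectomy. Section 12.1 has a core laboratory read all angiograms against the eligibility criteria and endpoints. Section 12.2 describes "adjudication of any events that may be considered serious and/or device related by the principal investigator and/or study Sponsor".

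**Analysis.** Section 4.2 allows up to 10 subjects. Section 8 is descriptive, without hypothesis tests.

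**The concern.** The same type of injury is judged on one scale at entry and on another as an outcome, and no text maps the two. A subject whose target lesion was dissected by a pre-dilation balloon could be admitted because flow is preserved, although the dissection is already of the grade that the protocol itself labels clinically significant. The rotating device then works in that segment.

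If the angiogram after atherectomy again shows grade C or greater, the classification is awkward. The device may have added an injury at the same site without changing the grade, or it may have extended the dissection to a higher grade. No sentence says whether either is a new on-set MAE. At stake is the main safety proportion of a first-in-human study, in which each subject is worth 10 percentage points.

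**Working it through.** The plan gives no figure to reproduce: there is no power calculation, performance goal or expected event rate. The check is a reading of the rules, followed by a calculation for scale.

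**1. Which routes to entry with a dissection are open?**
- Guidewire crossing: closed. Inclusion 9 requires crossing without complications.
- Treatment of a non-target lesion: closed. Under section 6.5.2 any angiographic complication there makes the subject an angiographic screening failure.
- Pre-dilation of the target lesion: open. Section 6.5.1 foresees it, and exclusion 19 tolerates a non-flow-limiting dissection.

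The other angiographic MAE components have no such exception. Distal embolization falls under exclusion 13, and a marketed-device perforation or pseudoaneurysm under exclusion 19 itself.

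**2. Is an unchanged pre-device dissection an MAE?** Most naturally not. The endpoint covers new on-set events, section 11 starts the clock at treatment, and section 11.4 sets aside what was present before atherectomy.

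**3. What is left open?** Section 11.4 makes worsening an adverse event but does not say whether a rise from grade C to a higher grade is a new on-set MAE. Nor does the plan expressly require an NHLBI grade on the pre-device image, which is the comparison needed to decide.

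**4. Effect of one such case at n = 10** (exact Clopper-Pearson 95% intervals):
- Not counted: 10/10 = 100%. Lower limit 0.025^(1/10) = 0.692, so 69.2 to 100%.
- Counted: 9/10 = 90%. Limits are the 0.025 quantile of Beta(9, 2) = 0.555 and the 0.975 quantile of Beta(10, 1) = 0.975^(1/10) = 0.997, so 55.5 to 99.7%.

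**5. How often might it arise?** The documents give no rates, so a, b and c are all assumptions.

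| Quantity | Low | Middle | High |
|---|---|---|---|
| a: target lesion pre-dilated | 0.20 | 0.35 | 0.50 |
| b: tolerated dissection of grade C or greater, among those | 0.02 | 0.05 | 0.10 |
| c: still grade C or greater after the device, among those | 0.50 | 0.75 | 1.00 |
| Enters at grade C or greater, a × b | 0.4% | 1.75% | 5.0% |
| Enters and persists, p = a × b × c | 0.2% | 1.31% | 5.0% |
| At least one in 10, 1 − (1 − p)^10 | 2.0% | 12.4% | 40.1% |

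Within each column the last row is an upper limit on cases that are hard to attribute, because the two images will settle some of them. If no non-flow-limiting dissection reaches grade C, then b = 0 and every result is zero.

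**The case against.** The strongest reply is that the rules already work. A reader might infer that a subject admitted at grade C is automatically an MAE, so that the device is charged with a balloon injury. The documents do not support that: the new on-set qualifier, the start of the adverse event period in section 11 and the rule in section 11.4 all point the other way.

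A reader might also infer that device injury and balloon injury can never be told apart in such a subject. That goes too far. Section 6.5.1 calls for images after pre-dilation and after atherectomy. The core laboratory reads all angiograms, the sponsor as well as the investigator can refer an event, and the adjudicator decides with all films in hand whether it contributes to the endpoint. A dissection blamed on the balloon is therefore not bound to be missed.

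Nor does the caution in section 6.5.3 to stop when a dissection is detected show a contradiction with exclusion 19. In context it most naturally concerns dissections that arise during device treatment, and the instructions for use take precedence over that summary.

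Two further points stand. The protocol does not define the NHLBI grades, so it does not show that a grade C dissection can be non-flow limiting. Flow limitation for entry and grade for outcome can also be defended as a design choice. None of this supplies a grade limit at entry or a rule for a tolerated dissection that progresses.

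**Conclusion.** The point holds in a limited form. The text does not bar entry with a target-lesion dissection already at the endpoint's grade, and it has no specific rule for classifying further injury at that site. Whether such a subject will occur is an assumption, since the documents neither define the grades nor give rates.

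If one does occur and its classification is disputed, freedom from MAE is 100% or 90% at the maximum sample size, and Procedure Success may move with it. No error rate or decision rule is affected, because the analysis is descriptive. Severity is minor; the change is worth making because it is cheap, and because it keeps a first-in-human rotating device out of a vessel with a dissection of the grade that the protocol calls clinically significant.

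**What to change.** 1. In exclusion 19 (section 6.1.2 and the synopsis), limit the exception to non-flow-limiting dissections below NHLBI grade C, judged on the angiogram taken before driveshaft introduction. Record a subject above that limit as an angiographic screening failure, as section 6.5.2 does for non-target complications. Say explicitly that this subject is not enrolled: section 6.5.1 can be read as enrolling at guidewire crossing, section 6.3 only at treatment with the device.
2. In section 5.1, state that a dissection is new on-set if, on an angiogram after driveshaft introduction and compared with the pre-device image, it first reaches grade C or greater, or increases in grade at C or above. An unchanged dissection then does not count, and a progressing one does. The second limb still matters if an entry dissection is later read as grade C.

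**Cost.** The change is one clause in two places, one sentence in section 5.1 and an NHLBI grade on the pre-device image. The images are already on the section 6.5.1 list. Under the assumptions above, 0.20 × 0.02 = 0.4% to 0.50 × 0.10 = 5.0% of otherwise eligible subjects would not be treated, or 0.04 to 0.5 subjects per 10. If the categories never overlap, nobody is lost.
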